10.3 Serious Adverse Events

When the principal investigator has determined that a Serious Adverse Event has occurred, the principal investigator is responsible for providing all Serious Adverse Events to BMS within 24 hours of this determination and to the IRB as per local policy. This applies to initial and follow-up information.

Follow-up Reports:

- The Investigator should take all appropriate measures to ensure the safety of the patients, notably he/she should follow up the outcome of any Serious Adverse Event and complete follow-up forms as necessary. The patient must be followed up until recovery, stabilization or return to baseline. This may mean that follow-up will continue after the patient has completed the trial and that additional investigations may be necessary.
- Any reportable Serious Adverse Events brought to the attention of the Investigator at any time after cessation of the trial and considered by him/her to be reasonably associated with medication administered during the period should also be submitted to the IRB (as required per local policy) and to BMS ([contact]; [contact]).
- As with the initial submission to the IRB, the principal investigator is also responsible for providing all follow-ups of Serious Adverse Events to the IRB (as required per local policy) and to BMS, using CIOMs or Medwatch form FDA 3500AA.

10.3.1 Subsite/External Participating Site SAE Reporting Requirement.

NOTE: External participating sites are not permitted to report directly to the OSU IRB or FDA. All external site SAEs are to be reported to the OSU Principal Investigator and Multi-Center Trial Program (MCTP). The MCTP will facilitate submission of external site SAEs to the OSU IRB and FDA.

All serious adverse events (SAEs) and other adverse events must be recorded on case report forms. In addition, all SAEs must be reported to the OSU Principal Investigator and MCTP within 24 hours of knowledge of the event using the FDA MedWatch 3500A mandatory reporting form and the "SAE Submission Form" cover sheet (refer to the Supplemental Forms Document).

Copies of de-identified source documentation pertaining to the SAE must be submitted to OSU. If a patient is permanently withdrawn from the study because of a SAE, this information must be included in the initial or follow-up SAE report form.

All SAEs must be submitted to the local IRB per local IRB and institutional policy.

Upon request of additional data or information that is deemed necessary must be reported to OSU as soon as possible but no later than 5 calendar days.

10.4 Reporting of Adverse Event Information Following Study Completion

Collection of safety information following the end of investigational product administration is important in assisting in the identification of possible delayed toxicities or withdrawal effects. All SAEs must be collected following the subject's written consent to participate in the study through 100 days of discontinuation of dosing and must be reported to BMS Worldwide Safety.

10.5 Pregnancy Statement and Use in Nursing Women

All women of childbearing potential MUST have a negative pregnancy test as required by the RevAssist program. If the pregnancy test is positive, the patient must not receive any investigational product and must not be enrolled in the study.

If, following initiation of the investigational product, it is subsequently discovered that a study subject is pregnant or may have been pregnant at the time of investigational product exposure, including during at least 6 half lives after product administration, the investigational product will be permanently discontinued in an appropriate manner (eg, dose tapering if necessary for subject safety).

The investigator must immediately notify Worldwide Safety @BMS of this event via the Pregnancy Surveillance Form in accordance with SAE reporting procedures. Follow-up information regarding the course of the pregnancy, including perinatal and neonatal outcome and, where applicable, offspring information must be reported on the Pregnancy Surveillance Form [provided upon request from BMS] any pregnancy that occurs in a female partner of a male study participant should be reported to BMS. Information on this pregnancy will be collected on the Pregnancy Surveillance Form.

Definition of Childbearing Potential: For the purposes of this study, a female of childbearing potential is a sexually mature female who: 1) has not undergone a hysterectomy (the surgical removal of the uterus) or bilateral oophorectomy (the surgical removal of both ovaries) or 2) has not been naturally postmenopausal for at least 24 consecutive months (i.e., has had menses at any time during the preceding 24 consecutive months).

Thalidomide, an analog of lenalidomide causes fetal harm and birth defects when administered to a pregnant woman. There are, however no adequate and well-controlled studies of lenalidomide in pregnant women. In New Zealand white rabbits at 10 and 20 mg/kg/day, lenalidomide was maternally toxic (reduced body weight gain and feed consumption; at 20 mg/kg/day, weight loss and one abortion). Developmental toxicity at 10 and 20 mg/kg/day included reduced fetal body weights and increased post implantation losses and fetal variations (morbidity/purple-discolored skin, undeveloped intermediate lung lobe, irregular nasal-frontal suture, and delayed metacarpal ossification)⁴⁵. The maternal and developmental no observed adverse effect levels (NOAELs) was 3mg/kg/day.

If the drug is used during pregnancy, or if the patient becomes pregnant while taking this drug, the patient should be apprised of the potential hazard to the fetus.

During the course of the trial, all patients of childbearing potential should be instructed to contact the treating physician immediately if they suspect they might have conceived a child. In addition, a missed or late menstrual period should be reported to the treating physician. If a female patient or the treating physician suspects that the female patient may be pregnant prior to administration of study drugs, the study drugs must be withheld until the results of a pregnancy test are available. If pregnancy is confirmed the patient must not receive study medications and must be withdrawn from the study. Throughout the entire pregnancy, additional contact should be made with the patient, and in some cases with the healthcare provider, to identify spontaneous abortions and elective terminations, as well as any medical reasons for elective termination. In addition, the study investigator should include perinatal and neonatal outcome. Infants should be followed for a minimum of 4 weeks.

If a male patient is suspected of having fathered a child while on study drugs, the pregnant female partner must be notified and counseled regarding the risk to the fetus. In addition, the treating physician must follow the course of the pregnancy, including prenatal and neonatal outcome. Infants should be followed for a minimum of eight weeks.

Upon live-birth delivery, the minimum information that should be collected includes date of birth, length of pregnancy, sex of infant, major and minor anomalies identified at birth. Outcomes can be obtained via mailed questionnaires, maternal interviews, medical record abstraction, or a combination of these methods. All serious adverse event reports relating to the pregnancy, including spontaneous abortion, elective abortion and congenital anomalies, should be forwarded to the FDA & BMS. (See Safety reporting section).

It is not known whether lenalidomide or nivolumab is excreted in human milk. Because many drugs are excreted in human milk and because of the potential for serious adverse reactions in nursing infants from lenalidomide, a decision should be made whether to discontinue nursing or discontinue the drug, taking into account the importance of the drug to the mother.

10.6 Data Safety Monitoring Plan

The data and safety monitoring plan will involve the continuous evaluation of safety, data quality and data timeliness. Investigators will conduct continuous review of data and patient safety at their regular Disease Group meetings (at least monthly) and the discussion will be documented in minutes. For each dose level, the Principal Investigator, study coordinator, and statistician, in consultation with treating physicians as appropriate will review all toxicities at a given dose level to inform the model for dose level adjustments. The Principal Investigator of the trial will review toxicities and responses of the trial where applicable at these disease center meetings and determine if the risk/benefit ratio of the trial changes. Frequency and severity of adverse events will be reviewed by the Principal Investigator and compared to what is known about the agent/device from other sources; including published literature, scientific meetings and discussions with sponsors, to determine if the trial should be terminated before completion. Serious adverse events will be reviewed by the OSUCCC Data and Safety Monitoring Committee (DSMC). The Principal Investigator will also submit progress reports that will be reviewed by the committee per the DSMC plan. All reportable SAEs will be reported to the IRB of record as per the policies of the IRB.

Mandatory safety and trial review teleconferences will be scheduled and moderated by the Multi-Center Trial Program (MCTP). All sites involved in the study are expected to have a representative present for every call to review and discuss patients on study and other applicable agenda items. Meeting minutes will be used to document each teleconference. The minutes will be stored in the MCTP protocol files. Teleconferences must minimally be held monthly and may be held more frequently, as needed. For studies closed to accrual with patients expected to remain on long-term

treatment and/or follow-up, teleconferences may be extended to occur every two months or quarterly. Decreasing frequency of teleconferences requires OSU PI and MCTP approval.

10.7 Data Submission

The study will be managed per the Multi-Center Trial Program (MCTP) policies. Subsite data must be submitted to the MCTP as outlined in the protocol-specific monitoring plan. The protocol-specific monitoring plan will be provided by the MCTP to external participating sites prior to site activation. Data will be submitted using case report forms and the Data Submission Form cover sheet (refer to Supplemental Forms Document) supplied by the MCTP. Access to the OSU OnCore database may be provided to external participating sites for direct electronic data entry. All data submitted must be accompanied by supporting source documents, where applicable and as outlined in the protocol-specific monitoring plan.

10.8 Auditing

As the study sponsor, The Ohio State University Comprehensive Cancer Center (OSUCCC) will audit each site as per OSU policies. Audits will be performed by the OSUCCC Clinical Research Audit Team. For sites with an auditing mechanism in place that are able to share documentation of their auditing standards and processes followed, an agreement may be requested for the site to perform local auditing and provide formal audit reports to the OSUCCC Multi-Center Trial Program (MCTP) and the Quality Assurance Oversight Committee.

10.9 Study Termination

The investigator may discontinue the trial at any time. Reasons for early trial discontinuation may include, but are not limited to, unacceptable toxicity of study treatment, a request to discontinue the trial from a regulatory authority or an IRB, or poor enrollment.

		70	Cares for self, unable to carry on normal activity or to do active work.
2	In bed <50% of the time. Ambulatory and capable of all self-care, but unable to carry out any work activities. Up and about more than 50% of waking hours.	60	Requires occasional assistance, but is able to care for most of his/her needs.
		50	Requires considerable assistance and frequent medical care.
3	In bed >50% of the time. Capable of only limited self-care, confined to bed or chair more than 50% of waking hours.	40	Disabled, requires special care and assistance.
		30	Severely disabled, hospitalization indicated. Death not imminent.
4	100% bedridden. Completely disabled. Cannot carry on any self-care. Totally confined to bed or chair.	20	Very sick, hospitalization indicated. Death not imminent.
		10	Moribund, fatal processes progressing rapidly.
5	Dead.	0	Dead.

13 Appendix. IMWG Response Criteria

Serum and urine M-protein estimates will be performed every 4 weeks; except for assessment of CR, patients with measurable disease restricted to the SPEP (or UPEP) will need to be followed only by SPEP (or UPEP). Responses will be assessed according to the criteria of the International Myeloma Working Group⁴⁶, and characterized as follows:

Response Category	Response Criteria ^a
SCR	CR as defined below plus 
 • Normal FLC ration and • Absence of clonal cells in bone marrow^b by immunohistochemistry or immunofluorescence^c
CR	Negative immunofixation on the serum and urine and disappearance of any soft tissue plasmacytomas and $\leq 5\%$ plasma cells in bone marrow ^b
VGPR	Serum and urine M-protein detectable by immunofixation but not on electrophoresis or 90% or greater reduction in serum M-protein plus urine M-protein level < 100 mg per 24 hours
PR	$\geq 50\%$ reduction of serum M-Protein and reduction in 24 hour urinary M-protein by $\geq 90\%$ or to < 200 mg per 24 hours If the serum and urine M-protein are unmeasurable ^d a $\geq 50\%$ decrease in the difference between involved and uninvolved FLC levels is required in place of the M-protein criteria If serum and urine M-protein are unmeasurable, and the serum free light assay is also unmeasurable, $\geq 50\%$ reduction in plasma cells is required in place of M-protein provided baseline bone marrow plasma cell percentage was $\geq 30\%$ In addition to the above, if present at baseline a $\geq 50\%$ reduction in the size of soft tissue plasmacytomas is also required
SD^e	Not meeting criteria for CR, VGPR, PR, or progressive disease
Relapse Category^f	Relapse Criteria
Progressive disease	Requires only one of the following: Increase of $\geq 25\%$ from baseline in: 
 • Serum M-component and/or (the absolute increase must be ≥ 0.5 g/dl)^g • Urine M-component and/or (the absolute increase must be ≥ 200 mg/24 hours) • In patients without measurable serum and urine M-protein levels the difference between involved and

	
uninvolved FLC levels, the absolute increase must be $> 10 \text{ mg/dl}$.
 
 • Bone marrow plasma cell percentage, the absolute % must be $\ge 10\%$^h. • Definite development of new bone lesions or soft tissue plasmacytomas increase in the size of existing bone lesions or soft tissue plasmacytomas. • Development of hypercalcemia (corrected serum calcium $> 11.5 \text{ mg/dl}$ or 2.65 mmol/l) that can be attributed solely to the plasma cell proliferative disorder.
Clinical relapse (Not used for TTP or PFS)	Clinical relapse requires one or more of: 
 • Development of new soft tissue plasmacytoma or bone lesions • Definite increase in the size of existing plasmacytomas or bone lesions. A definite increase is defined as a 50% (and at least 1 cm) increase as measured serially by the sum of the products of the cross-diameters of the measurable lesion • Hypercalcemia ($> 11.5 \text{ mg/dl}$ [2.65 mmol/l]) • Decrease in hemoglobin of $\ge 2 \text{ g/dl}$ (1.25 mmol/l) • Rise in serum creatinine by 2 mg/dl or more ($177 \mu\text{mol/l}$ or more)
Relapse from CR ⁱ	Any one or more of the following: 
 • Reappearance of serum or urine M-protein by immunofixation or electrophoresis • Development of $\ge 5\%$ plasma cells in the bone marrow^j • Appearance of any other sign or progression

a. All response categories require two consecutive assessments made at anytime before the institution of any new therapy; all categories also require no known evidence of progressive or new bone lesions if radiographic studies were performed. Radiographic studies are not required to satisfy these response criteria.

b. Confirmation with repeat biopsy not necessary.

c. Presence/absence of clonal cells is based upon the κ/λ ratio by immunohistochemistry and/or immunofluorescence requires a minimum of 100 plasma cells for analysis. An abnormal ration reflecting presence of an abnormal clone is κ/λ of $> 4:1$ or $< 1:2$.

d. Applicable only to patients who have 'measurable' disease defined by at least one of the following three measurements: Serum M-protein $\ge 1 \text{ g/dl}$, Urine M-protein $\ge 200 \text{ mg/24hour}$, Serum FLC assay involved FLC level $\ge 10 \text{ mg/dl}$ provided serum FLC ration is abnormal.

e. Not recommended for use as an indicator of response; stability of disease is best described by providing the time to progression estimates).

f. All relapse categories require two consecutive assessments made at anytime before classification as relapse or disease progression and/or the institution of any new therapy.

g. For progressive disease, serum M-component increases of $\ge 1 \text{ gm/dl}$ are sufficient to define relapse if starting M-component is $\ge 5 \text{ g/dl}$.

h. Relapse from CR has the 5% cutoff versus 10% for other categories or relapse.

i. To only be used if the end point studied is disease free survival. For purposes of calculating time to progression and progression-free survival, CR patients should also be evaluated using criteria listed above for progressive disease.

j. Relapse from CR has the 5% cutoff versus 10% for other categories of relapse.

14 Appendix. NYHA Cardiac Disease

Class	Functional Capacity	Objective Assessment
I	Patients with cardiac disease but without resulting limitations of physical activity. Ordinary physical activity does not cause undue fatigue, palpitation, dyspnea, or anginal pain.	No objective evidence of cardiovascular disease.
II	Patients with cardiac disease resulting in slight limitation of physical activity. They are comfortable at rest. Ordinary physical activity results in fatigue, palpitation, dyspnea, or anginal pain.	Objective evidence of minimal cardiovascular disease.
III	Patients with cardiac disease resulting in marked limitation of physical activity. They are comfortable at rest. Less than ordinary activity causes fatigue, palpitation, dyspnea, or anginal pain.	Objective evidence of moderately severe cardiovascular disease.
IV	Patients with cardiac disease resulting in inability to carry on any physical activity without discomfort. Symptoms of heart failure or the anginal syndrome may be present even at rest. If any physical activity is undertaken, discomfort is increased.	Objective evidence of severe cardiovascular disease.

Source: The Criteria Committee of New York Heart Association. Nomenclature and Criteria for Diagnosis of Diseases of the Heart and Great Vessels. 9th Ed. Boston, MA: Little, Brown & Co; 1994:253-256.

15 Appendix. FACT/GOG-Neurotoxicity

By circling one (1) number per line, please indicate how true each statement has been for you during the past 7 days.

ADDITIONAL CONCERNS	Not at all	A little bit	Some-what	Quite a bit	Very much
I have numbness or tingling in my hands.....	0	1	2	3	4
I have numbness or tingling in my feet.....	0	1	2	3	4
I feel discomfort in my hands.....	0	1	2	3	4
I feel discomfort in my feet.....	0	1	2	3	4
I have joint pain or muscle cramps.....	0	1	2	3	4
I feel weak all over.....	0	1	2	3	4
I have trouble hearing.....	0	1	2	3	4
I get a ringing or buzzing in my ears.....	0	1	2	3	4
I have trouble buttoning buttons.....	0	1	2	3	4
I have trouble feeling the shape of small objects when they are in my hand.....	0	1	2	3	4
I have trouble walking.....	0	1	2	3	4

Sources: Cella DF, Tulsky DS, Gray G, Sarafian B, Lloyd S, Linn E, et al. The functional assessment of cancer therapy (FACT) scale: development and validation of the general measure. *J Clin Oncol* 1993;11(3):570-79.

16 Appendix. Ethical and regulatory

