3 ELIGIBILITY CRITERIA

3.1 Inclusion Criteria

- Patients must be at least 18 years of age with evidence of progression, relapse or refractory disease from last line of therapy as defined by IMWG criteria. A line of therapy is defined as one or more cycles of a planned treatment program which may be one therapy or a sequence of treatments. A new line of therapy begins when a planned course of therapy is modified due to disease progression, relapse or toxicity or when a planned period of observation off therapy.
Measurable disease as defined by any of the following:
 - Serum M-protein ≥ 0.5 g/dl (≥ 10 g/l)
 - Urine monoclonal protein ≥ 200 mg/24h
 - Involved FLC level ≥ 10 mg/dl (≥ 100 mg/l) and an abnormal serum free light chain ratio (<0.26 , or >1.65)
 - Measurable biopsy proven plasmacytoma (should be measured within 28 days of initial investigational agent dosing)
- Patients must have exhausted all available therapies known to provide clinical benefit and has progressed, relapsed or is refractory to last line of treatment.
- Patients must have had at least 4 prior lines of therapy.
- Patient may be enrolled at any time from last line of therapy.
- Patients must have ANC $> 1000/\mu\text{L}$; Platelets $\geq 75,000/\mu\text{L}$, if plasma cell percentage on bone marrow biopsy aspirate or core is $> 30\%$, platelet eligibility requirement will be adjusted to $60,000/\mu\text{L}$.
- Patients must have adequate hepatic function as evidenced by: total bilirubin ≤ 1.5 mg/dL, alkaline phosphatase $\leq 3X$ the ULN, AST/ALT $\leq 2X$ the ULN
- Patients must have adequate renal function as evidenced by serum creatinine ≤ 2 mg/dL or calculated creatinine clearance of ≥ 40 ml/min within 14 days of registration using MDRD formula.
- Patient must be able to swallow capsule or tablet.
- Patients must provide informed consent.
- Patients must have a left ventricular ejection fraction $\geq 30\%$, no uncontrolled arrhythmias or New York Heart Association class III-IV heart failure.
- Patients must have a Karnofsky performance status ≥ 70 .
- A negative pregnancy test will be required for all women of child bearing potential. Breast feeding is not permitted.
- Fertility requirements
 - Female patients with child bearing potential must have a negative pregnancy test at least 7 days before starting treatment drugs.
 - Male patients must agree to use an adequate method of contraception for the duration of the study and for 7 months afterwards.

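### Appendix 13 lets some patients enrolled on light chains alone be scored VGPR, and a few CR, with unchanged disease, and VGPR lacks the plasmacytoma clause that PR has

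*Combined protocol and SAP*

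**What the plan says.** **Entry.** Section 3.1 accepts "Measurable disease as defined by any of the following", followed by four alternatives. One is "Involved FLC level ≥ 10 mg/dl (≥ 100 mg/l) and an abnormal serum free light chain ratio"; another is "Measurable biopsy proven plasmacytoma". A patient can therefore enter on light chains alone or on a plasmacytoma alone.

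**Response (Appendix 13, IMWG Response Criteria).**
- CR: "Negative immunofixation on the serum and urine and disappearance of any soft tissue plasmacytomas and" at most 5% plasma cells in the marrow. There is no FLC term; a normal FLC ratio is asked for only in sCR.
- VGPR: "Serum and urine M-protein detectable by immunofixation but not on electrophoresis", or a serum M-protein fall of at least 90% with urine M-protein under 100 mg per 24 hours. There is no FLC term and no plasmacytoma term.
- PR: where serum and urine M-protein cannot be measured, a 50% "decrease in the difference between involved and uninvolved FLC levels is required in place of the M-protein criteria". If a plasmacytoma was present at baseline, a 50% "reduction in the size of soft tissue plasmacytomas is also required".
- SD is whatever meets none of CR, VGPR, PR or progression.

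**Use.** Sections 2.1 and 2.3 make the response rate after 4 cycles the primary endpoint. Section 7.1.1 counts partial and complete responses and applies the rule for 18 patients: 7 or fewer is ineffective, 10 or more is effective, and 8 or 9 is inconclusive.

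**The concern.** The first limb of VGPR can be true before the first dose. For a patient followed by a measurable serum or urine M-protein this does little harm, because the protein has to fall to reach that state. An FLC-only patient may have had so little intact M-protein from the start that the state already holds, and the marker that actually tracks the disease is not consulted. The CR row has the same weakness in a narrower group.

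The plasmacytoma omission is a separate fault. It makes the higher grade easier to reach than the lower one for a patient whose plasmacytoma has not shrunk.

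The trial is single-arm with 18 patients, and its decision turns on a few responses. Responses that need no treatment effect push the count toward the effective boundary and away from rejection.

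**Working it through.** **1. Can unchanged disease meet the rows?**

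Take an FLC-only patient whose M-protein, in serum and urine, shows on immunofixation but not on electrophoresis at baseline, and whose FLC then stays constant.
- PR: not met, because the FLC difference has not halved.
- Progression: not met. In such patients it needs a rise in the FLC difference of at least 25% and more than 10 mg/dl.
- VGPR, first limb: met at every assessment.
- SD: excluded, because it is residual and VGPR is met.
- Footnote a: asks for two assessments in a row and no known new or progressive bone lesions. Both can hold without change.
- Footnote d: attached to the word for unmeasurable in the PR row. Even applied to every row, an FLC-only patient satisfies it through the FLC measure.

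No rule says that VGPR or CR must first meet PR, so the printed result is VGPR. If the same patient instead has negative immunofixation in serum and urine, at most 5% marrow plasma cells and no plasmacytoma, the printed result is CR. A plasmacytoma-only patient in the first-limb state also meets VGPR with the lesion unchanged, but cannot meet CR, which requires its disappearance.

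**2. VGPR against PR with an unchanged plasmacytoma**

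| Serum M-protein fall | Urine M-protein | Plasmacytoma | Printed category |
|---|---|---|---|
| 90% | below 100 mg/24 h | unchanged | VGPR |
| 60% | below 200 mg/24 h | unchanged | not PR |

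**3. The plan's own figures (section 7.1.1)**

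Inputs: n = 18, inactive rate 26%, active rate 60%, boundaries 7 and 10, alpha 5%, beta 5%, correct rejection 80%. Exact binomial results:
- P(10 or more at 26%) = 0.0073, against alpha 0.05
- P(7 or fewer at 60%) = 0.0576, against beta 0.05
- P(7 or fewer at 26%) = 0.930, against 0.80
- P(10 or more at 60%) = 0.737

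The stated rates are not reproduced exactly. That is a separate matter, but the slack at 26% is what absorbs a small k below.

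**4. Effect of k automatic responders**

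Assume k of the 18 score automatically and the other 18 − k respond at 26%.
- P(effective) = P(Bin(18 − k, 0.26) ≥ 10 − k)
- P(ineffective) = P(Bin(18 − k, 0.26) ≤ 7 − k)
- Expected response rate = (k + 0.26 × (18 − k)) / 18

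| k | Expected rate | P(10 or more) | P(8 or 9) | P(7 or fewer) |
|---|---|---|---|---|
| 0 | 26.0% | 0.7% | 6.3% | 93.0% |
| 1 | 30.1% | 1.6% | 11.1% | 87.3% |
| 2 | 34.2% | 3.4% | 18.3% | 78.3% |
| 3 | 38.3% | 6.8% | 27.9% | 65.3% |
| 4 | 42.4% | 13.0% | 38.4% | 48.6% |

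Alternatively, let each patient independently have probability f of scoring automatically, so the response rate is f + 0.26 × (1 − f). P(10 or more) and P(7 or fewer) are then 2.0% and 86.6% for f = 5%, 4.4% and 77.5% for f = 10%, 8.6% and 66.2% for f = 15%, and 15.1% and 53.6% for f = 20%.

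**The case against.** **The table may only summarise the IMWG criteria.** The appendix cites the published criteria, which may contain FLC or nesting rules that the table leaves out. That source was not available, so how sites would score in practice is not established. The protocol nevertheless prints the table as its own characterisation of response, and the printed rows have the gap. The objection lowers confidence in the harm, not in the reading.

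**A reader might infer that any light-chain-only patient scores automatically.** The rows do not say so. A patient with a sub-threshold band visible on electrophoresis does not meet the first VGPR limb, nor does one with negative immunofixation. Read strictly, the limb needs detection in both serum and urine. CR also demands a nearly clear marrow and no plasmacytoma, which should be uncommon in patients with at least 4 prior lines who have progressed, relapsed or are refractory.

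**A reader might count the 90%-fall plasmacytoma example as response without drug effect.** It is not: a 90% M-protein fall is a real change, and growth of an existing plasmacytoma is already progression. That example is an ordering fault between grades and is not part of the figures for k.

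**Section 7.3 makes the point moot.** Its response rate counts SD, so an unchanged patient is a responder whatever the VGPR row says. This is right for that definition. The concern therefore rests on section 7.1.1, and the two sections must be reconciled separately. Once SD is excluded, this gap remains as a way for unchanged disease to count.

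**Conclusion.** The gap is real in the printed rows and should be fixed. It covers a subset: FLC-only patients who are immunofixation-positive and electrophoresis-negative at baseline (VGPR), and a smaller group for CR. The missing plasmacytoma clause in VGPR stands as a separate inconsistency.

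The size depends on k, and the documents give no share of such patients. At k = 1 both error properties stay within the stated limits. At k = 2 correct rejection is 78.3%, just under 80%, with the false-positive rate still at 3.4%. From k = 3 the 5% alpha is exceeded as well. It would go too far to conclude that the decision rule fails; the documents support only that it could, if two or more of 18 patients are of this kind.

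The result assumes that the table is applied as printed, that section 7.1.1 governs, that VGPR counts there as a grade of partial response, and that all other patients respond at 26%.

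**What to change.** In Appendix 13, state that:

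1. CR and VGPR count as response only with at least PR-level improvement from baseline on the measure that qualified the patient under section 3.1: serum M-protein, urine M-protein, FLC difference or, for plasmacytoma-only patients, plasmacytoma size. The last must stand alone, because the PR row has plasmacytoma reduction only as an added condition; without it these patients could not be scored CR or VGPR.
2. In FLC-only patients, CR also needs the normal FLC ratio already used in sCR, and VGPR needs a stated fall in the involved-minus-uninvolved FLC difference. A fall of at least 90% would match the row's M-protein threshold; it is an example, as the documents give no FLC figure for VGPR.
3. The PR plasmacytoma clause (at least 50% reduction if present at baseline) also applies to VGPR.

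Align footnote d's serum threshold (1 g/dl) with section 3.1 (0.5 g/dl), so that measurable has one meaning. In doing so, settle section 3.1 itself: its bracketed 10 g/l equals 1 g/dl, not 0.5 g/dl.

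The cost is a few sentences. FLC is already measured on day 1 of each cycle (section 6.9.6, note i), so no test is added. The observed response rate may be slightly lower.
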